5.6 Administration Instructions

- 5.6.1 The forms must be administered at the time points noted in Table 1 (Section [7](#)).
- 5.6.2 The CRA should read the instructions at the beginning of each questionnaire and administer to the patient unless the patient chooses to complete the survey on her own. The patient should be instructed to respond to questions in terms of her experience during the time frame specified on the form. It is permissible to assist the patient with completion of the forms, as long as the staff person does not influence the patient's response.
- 5.6.3 The completed forms must be reviewed by the designated CRN or CRA, as soon as the patient completes them, to ensure all items were marked appropriately. If more than one answer was marked, the patient should be asked to choose the answer which best reflects how she is feeling. If a question was not answered, the patient should be asked if she would like to answer it. The patient should always have the option to refuse. If the patient refuses, it should be indicated on the form that she declined to answer the item.
- 5.6.4 If the patient cannot complete the baseline form properly, the reason should be noted on the Assessment Compliance Form. If a patient cannot complete the follow-up questionnaire because she is too sick AND the CRN/CRA learns of it, it will be documented on the Assessment Compliance Form.

Rev. 11/16

- 5.6.5 The clinician responsible for filling out the **Provider Reproductive Health Values Surveys (Specific to Patient)** may be the treating MD, the nurse practitioner, or PA-C involved in the clinical care of the patient. This will be determined per patient by the CRA/CRN.
- 5.6.6 If overlap occurs between the patient study follow-up visit and chemotherapy/radiation treatment visit, the Patient Follow-up Interviews should be completed rather than the Patient Follow-up Interview During Chemotherapy.

Rev. Add11

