5.8 Provision of Appropriate Care for Patients

The clinical management of all patients (regardless of symptom severity) will be determined by the treating physician.

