Provider Consent Form	X				
Delegation of Responsibilities Log	X				
CLINICIAN					
Provider Reproductive Health Values Survey (General) ³	X		X		
Provider Reproductive Health Values Survey (Specific to Patient) ⁵		X			X
Medical Record Abstraction Form – Baseline ⁶		X			
Medical Record Abstraction Form – Follow-up ^{6,13}				X	X
Pregnancy Test ⁷		X		X	X
Pregnancy Supplemental Form ⁸		X		X	X
PATIENT					
Patient Baseline Interview ⁹		X			
Sexual Function Survey		X		X	X
Patient Interview - During Chemotherapy/Radiation Treatment ¹⁰				X	
Patient Follow-up Interview ^{11, 12}					X

1. Pre-Study documents should be completed prior to participant recruitment.
2. These documents need to be updated based on staffing and provider changes over the course of this study. We define provider as the clinician (MD, nurse practitioner or PA-C) that clinically assesses the oncology patient.
3. Each primary clinician should complete this form once at 0 (Prior to Study Training) and 30 months from site initiation. It is not necessary to fill out the form for each patient at each of these time points. As staffing changes over the course of this study new clinicians will complete this form

Rev. 11/16

Rev. Add8 upon signing provider consent and at 30 months from site initiation. The date for site initiation is defined as the time when the site is approved to enroll patients into this study.

Rev. Add10 4. Patient will have the baseline provider visit, complete baseline surveys and be registered to the trial on the same day of consent. If this is not feasible, then all baseline requirements (including registration) must be completed within one week of patient consent and before treatment initiation as part of their standard of care (i.e., chemotherapy or radiation therapy). Baseline provider visits, completion of baseline surveys and study registration must be completed on same day.

5. This form should be completed by the primary clinician after each office visit (as determined by the CRN/CRA)

6. Complete the medical record abstraction forms from the medical chart of each eligible participant after visit with the patient. Form must be completed and entered electronically in Medidata Rave within one week of patient visit.

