7. Pregnancy Test requirements. All patients must be counseled about pregnancy precautions, risks of fetal exposure and other risk as per standard of care. Pregnancy tests should be administered at Baseline, 3, 6, 12, and 24 months from Baseline Visit and within one (1) week prior to each chemotherapy regimen. For patients on radiation therapy (RT) alone, pregnancy tests should be administered within one (1) week prior to the initiation of radiation therapy then every four (4) weeks until the end of radiation treatment. For patients who aged past 55 after enrollment may discontinue pregnancy tests if menopause is confirmed FSH < 23mIU/mL. Patients who have had a hysterectomy after enrollment may also discontinue pregnancy tests. Pregnant patients may discontinue pregnancy tests until delivery

Rev. Add10 8. If patient is pregnant or has been pregnant since her last study visit, one Pregnancy Supplement Form should be completed for each pregnancy.

9. Interview done after visit with the provider.

10. Study surveys should be completed at the beginning of each regimen of cancer treatment. For patients undergoing chemotherapy, surveys should be administered within one (1) week prior to each chemotherapy regimen. For patients on radiation therapy (RT) alone, surveys should be administered within one (1) week prior to the initiation of radiation therapy then every four (4) weeks until the end of radiation treatment. Patients receiving both chemotherapy and RT must follow the chemotherapy reporting schedule; if patient's treatment overlaps (+/- 2 weeks), the questionnaires do not have to be repeated.

Rev. Add10 11. Sites must complete the study surveys within the following windows:

- 3-month visit: +/- one month
- 6-month visit: +/- one month
- starting from 12-month visits: +/- 2 months

12. If there is an overlap (+/- 2 weeks) of visits at 3, 6, 12, and 24 months and visits relating to chemotherapy or RT, the Medical Record Abstraction-Follow up, Patient Follow-up Interview, the Sexual Function Survey and the Pregnancy Test only need to be completed once at the 3, 6, 12, and 24 month visits and not at the chemotherapy or RT visits.

13. The term 'regimen' is defined as anytime a patient starts a new course of medical treatment

Table 2. Biological Sample Submissions

NOTE: Effective March 10, 2021 the endocrine marker sub-study is closed to further accrual. This sub study has met its targeted accrual goal.

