Serum specimens should continue to be collected from previously enrolled patients that have consented to provide serum specimens at the time points outlined below.

Do not submit serum specimens from patients registered to E1Q11 after March 10, 2021.

NOTE: THIS SECTION APPLIES TO BOTH STUDY ARMS.

Blood samples should be submitted for the endocrine markers as outlined in Section 9. Submit only from patients who have given written consent to participate in the optional laboratory studies.

NOTE: It is required that biological sample submissions be logged into the ECOG-ACRIN Sample Tracking System (STS) for purposes of monitoring compliance.

NOTE: Institutions must complete and submit the Quest Diagnostics Sub-Account Information Sheet ([Appendix III](#)) to create their study specific account number in order to obtain supplies and arrange for courier service for the collection of the blood samples. See Section 9 for further instructions.

Biological Materials	Day of Registration [prior to treatment] ¹	Within One Week Prior to Start of Each Chemotherapy Regimen or Every Four Weeks during RT ¹	At the end of 3, 6, 12, 24 Months from Baseline Visit
From Patients Who Answer "Yes" to "I agree to participate in the laboratory research studies that are being done as part of this clinical trial."³			
Serum (one 7.5mL red top tube) ^{2,3,4}	X	X	X
Serum, SST (one 7.5mL red/black top tube) ^{2,3,4}	X	X	X

1. For patients undergoing chemotherapy, blood samples will also be collected in conjunction with chemotherapy within one (1) week prior to the start of each chemotherapy regimen. For patients undergoing radiation therapy (RT) alone, blood samples will be collected within one (1) week prior to the initiation of radiation therapy and every four (4) weeks until the end of radiation treatment.
2. When possible, blood draws will be timed with the collection of blood draws for routine clinical purposes thus minimizing participant burden.
3. Ship blood samples to Quest Diagnostics as outlined in Section 9.
4. Supplies are available for the collection of the blood samples.

Rev. 11/17	8. Statistical Considerations

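### Table 1 footnote 12 lets a month-visit pregnancy test replace the pre-treatment test of footnote 7, even when it falls after treatment has started

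*Combined protocol and SAP*

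**What the plan says.** All of this is in the Arm A schedule (Section 7, Table 1) unless noted.

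- **Footnote 7** asks for pregnancy tests at baseline, at 3, 6, 12 and 24 months, "and within one (1) week prior to each chemotherapy regimen". Patients having RT alone are tested within a week before RT starts and every four weeks after that.
- **Footnote 12** sets the overlap rule: "If there is an overlap (+/- 2 weeks) of visits at 3, 6, 12, and 24 months" and chemotherapy or RT visits, "the Medical Record Abstraction-Follow up, Patient Follow-up Interview, the Sexual Function Survey and the Pregnancy Test only need to be completed once". The month-visit test is kept and the one at the chemotherapy or RT visit is dropped.
- **Footnote 10** has an overlap rule for patients receiving both chemotherapy and RT, limited to surveys: "the questionnaires do not have to be repeated".
- **Section 5.6.6** merges only interviews when a month visit and a treatment visit coincide: "the Patient Follow-up Interviews should be completed rather than the Patient Follow-up Interview During Chemotherapy".
- **Table 2, footnote 1** keeps the pre-regimen timing for the endocrine sub-study: "blood samples will also be collected in conjunction with chemotherapy within one (1) week prior to the start of each chemotherapy regimen". It has no overlap waiver.
- **Footnote 4** places the baseline requirements "before treatment initiation as part of their standard of care".
- **Section 5.8** says that clinical management "will be determined by the treating physician".

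**The concern.** The two footnotes set different timings for the same test. Footnote 7 ties it to the week before treatment. Footnote 12 removes that test when another visit is near, in either direction, and does not require the substitute to come before treatment. A site that follows footnote 12 as written can start a regimen or RT with no study-required pregnancy test in the preceding week.

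The population makes the timing relevant. Patients are pre-menopausal, aged 15 to 55, without prior hysterectomy, bilateral oophorectomy or sterilization (Section 3.1). Strata 1 and 2 are sexually active (Section 8.1). The background text itself raises teratogenic treatment (Section 1.5) and notes that many patients remain fertile during treatment (Section 1.7).

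A lesser effect concerns data. A merged Sexual Function Survey or chart abstraction completed after the start can stand in for the pre-regimen one, while the hypothesis in Section 1.8 is about change during treatment.

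**Working it through.** No sample size, power or error rate is involved. The check is interval arithmetic, with day 0 as the start of the regimen (or of RT, for RT alone).

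**Inputs**
- Required window for the test: days -7 to 0 (footnote 7), which is 8 calendar days.
- Overlap tolerance: 14 days either side (footnote 12).
- Test retained: the one at the month visit (footnote 12).

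The plan does not say whether the overlap is counted from treatment start or from the chemotherapy or RT visit, so both readings are shown.

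**Reading A: month visit m within 14 days of the start.** Then -14 ≤ m ≤ 14.

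**Reading B: month visit m within 14 days of a pre-treatment visit v, with v on days -7 to 0.** The earliest m is -7 - 14 = -21 and the latest is 0 + 14 = +14.

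| | Reading A | Reading B |
|---|---|---|
| Possible days for the retained test | -14 to +14: 29 | -21 to +14: 36 |
| Meets footnote 7 (days -7 to 0) | 8 | 8 |
| Too early | -14 to -8: 7 | -21 to -8: 14 |
| After the start (days +1 to +14) | 14 | 14 |
| Check | 8 + 7 + 14 = 29 | 8 + 14 + 14 = 36 |
| Share of calendar days meeting footnote 7 | 8/29 = 27.6% | 8/36 = 22.2% |

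**Examples, with the 3-month visit on day 91**
- *Regimen starts on day 77.* The only study-required test is at 91 - 77 = 14 days after the start. This is the extreme case. Under Reading B it arises only if the chemotherapy visit is on day 77 itself.
- *Regimen starts on day 84.* The test is at 91 - 84 = 7 days after the start. A pre-regimen visit anywhere in days 77 to 84 is 7 to 14 days from day 91, so the waiver applies under both readings.

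**Does other text restore the pre-treatment test?**
- Footnote 4 protects a first regimen begun within a week of the baseline test. It does not reach later regimens or a delayed start.
- Footnote 11 lets sites move the month visit (one month either way at 3 and 6 months, two months from month 12). One visit can therefore often serve both purposes, but nothing makes it do so.
- Footnote 7 also requires counselling to the standard of care, which sets no time for a test.
- Section 5.8 leaves management to the physician and requires no test.
- Section 5.6.6 and footnote 10 do not mention the pregnancy test.

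None of these closes the gap.

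**The case against.** The strongest reply is that this test does not gate treatment. Pregnant patients are eligible (Section 3.1.5), the trial gives no cancer therapy, and nothing in the visible text withholds treatment after a positive result. The study action is a supplement form (footnote 8). In footnote 7 the counselling is mandatory, while the tests are worded as what should be done. Footnote 12 names the pregnancy test expressly, so it can be read as a deliberate reduction of burden. It is also permissive: a site may test at both visits and satisfy both footnotes. The reach is narrow, because a regimen is a new course of treatment and only starts near a month visit are affected.

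Most of this stands, and it limits the weight of the point. No harm is shown, nor any displacement of clinical testing. The comparison with footnote 10 and Table 2 is only suggestive, since those rules serve other purposes. The four-weekly tests after RT has begun are on-treatment tests, and merging them raises no pre-treatment problem. The sexual function effect is small, and no conclusion is shown to depend on it.

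The conflict itself remains. Footnote 7 schedules a pre-treatment test although standard care exists alongside it, and footnote 12 drops that test without any condition on timing. Deliberate or not, the waiver permits a substitute taken after the start.

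**Conclusion.** The concern holds. In the overlap case the only study-required pregnancy test can come up to 14 days after treatment has begun, or 14 to 21 days before it depending on the reading, against a required window of 0 to 7 days before. The day counts describe what the wording allows and are not a probability; the documents do not say how often regimens start near a month visit. The finding is established for Arm A only, because the Arm B schedule is in Addendum I, which is not among the documents. It rests on a site using the waiver as written. The primary endpoint and power are not affected. It is a clear gap in the schedule that should be corrected because the correction is so cheap.

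**What to change.** Let footnote 7 govern. Either delete the Pregnancy Test from the footnote 12 list, or add that the month-visit test replaces the pre-treatment one only if it is taken 0 to 7 days before the regimen or RT starts. The retained test then always lies in days -7 to 0. Merging can stay for the surveys, the abstraction and the four-weekly tests after RT has begun. Make the same change in Addendum I if its wording matches. In the analysis, classify each merged Sexual Function Survey and abstraction as before or after regimen start by its actual date.

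The cost is one line, a site notice and an occasional extra routine test that footnote 7 already schedules. Patients in the blood-sample sub-study already have a draw in that week, so they need no extra contact. The sub-study was set at 200 patients, so of the 425 projected, about 425 - 200 = 225 are outside it. Some of these may need an added contact when the month visit cannot be moved into the window.

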8.2 Selection of Participating Clinics

To ensure patient diversity in this study, all NCI MU NCORPs will be invited to participate in this study. Once participating MU NCORPs have been identified, the remainder of sites will be filled by NCORPS. All institutions will be equally randomized to either the non-intervention group (Arm A) or the intervention group (Arm B). Each institution will have patients enrolled in one of the four strata depending on the patient’s pregnancy status, sexual activity status, and/or her birth intention.

8.3 Sample Size

To have a manageable number of patients in this study, the sample size is recalculated based on the primary endpoint. For a cluster randomized trial, we must take into account the similarity among responses within a cluster (known as the intracluster correlation coefficient (ICC); ICC=0 indicating individuals completely independent; ICC=1 indicating individuals completely dependent), the required number of clusters per arm (denoted as k), and the number of patients per cluster (denoted as m) for the sample size calculations. To account for the possibility of variable cluster size in real accrual, coefficient of variation (CV) of cluster sizes (defined as the ratio of standard deviation of cluster sizes to mean of cluster sizes) was considered in sample size calculations as well. In this section, the power is computed assuming equal enrollment per arm. As of January 4, 2021, though, 66% (268/406) of the enrollment is from sites on the control arm and 34% from sites in the intervention group (with recent accrual closer to 50% in each group, due to site accrual caps). The number of intervention arm cases needed under equal enrollment will then be used to determine the overall sample size under the enrollment proportions seen in this study. The actual power should then be higher than stated, given the additional enrollment on the control arm.

To detect an increase from 50% to 80% (across all four strata) in the adoption of appropriate reproductive health management within 3 months consistent with patient's initial reproductive health goals (the primary endpoint), Table 1 shows the power with respect to various parameter values (including intra-cluster correlation coefficient, number of clusters, coefficient of variation, and mean cluster size), assuming an exchangeable within-cluster correlation structure, t-distribution, and type I error rate (α) at 0.10 (two-sided). The sample size and power calculations were conducted using the Shiny CRT Calculator, a web-based tool (<https://clusterrcts.shinyapps.io/rshinyapp/>)^{24,25}.

Table 1: Power for Various Plausible Parameter Values (assuming an exchangeable within-cluster correlation structure, t-distribution, and $\alpha=0.10$)

Number of Clusters (k, per arm)	Coefficient of Variation (CV)	Mean Cluster Size (m)	ICC		
			0.05	0.10	0.15
8	0.0	11	0.96	0.90	0.84
	0.5	14	0.97	0.90	0.82
	0.6	16	0.97	0.90	0.81
	0.7	20	0.98	0.90	0.81
	0.8	15	0.95	0.85	0.75
	0.8	27	0.98	0.90	0.80
9	0.0	9	0.95	0.90	0.85
	0.5	11	0.96	0.90	0.83
	0.6	12	0.96	0.90	0.82
	0.7	14	0.97	0.90	0.82
	0.8	17	0.97	0.90	0.81
10	0.0	8	0.96	0.91	0.87
	0.5	9	0.96	0.90	0.84

Number of Clusters (k, per arm)	Coefficient of Variation (CV)	Mean Cluster Size (m)	ICC		
			0.05	0.10	0.15
	0.6	10	0.96	0.90	0.84
	0.7	11	0.97	0.90	0.83
	0.8	12	0.97	0.90	0.81

Based on the results in the Verma and Lê's study²⁶, it is estimated that the intra-cluster correlation coefficient for the primary endpoint is 0.10. As of January 4, 2021, 9 Arm A sites and 8 Arm B sites have had enrolled patients for the EROS trial (n=268 for Arm A and 138 for Arm B) with CV=0.78 (=23.9/18.6). Assuming ICC=0.10, 16 institutions in total (i.e., 8 clusters per arm) and CV=0.8, Table 1 indicates an average of 27 eligible patients per cluster can detect an improvement from 50% to 80% while keeping 0.10 two-sided type I error rate and 90% power. Due to the slow accrual in Arm B, the study power was lowered to 85% with an average of 15 eligible patients per cluster, keeping the other parameters constant. In this case, this study requires 240 eligible patients in total enrolled into this study (average of 15 per cluster, 120 per arm) in order to keep 0.10 type I error rate and 85% chance of detecting the proposed 50% to 80% improvement on the primary endpoint. Assuming a 5% ineligibility rate and an additional 15% of attrition rate at 3 months (based on the fourth interim analysis with data pulled in July 2019), the sample size for the primary endpoint of this study is inflated to 298 patients in total (149 patients per arm, across the four strata), under equal enrollment on the two arms. To obtain 149 intervention arm cases, total enrollment will need to be 425 patients (see below).

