8.4 Accrual Goal and Accrual Period

To help safeguard 10 enrolling sites per intervention group (as originally proposed), we have invited more than 20 MU NCORPs/NCORPs to participate in this study (as listed on the cover page of the protocol). To further help accrual, we lowered the age limit to 15 years in Addendum 9 (effective from February 6, 2019). Besides the original participating MU NCORPs/NCORPs, interested pediatric MU NCORPs/NCORPs are allowed to participate in the EROS trial as well.

To have adequate power to detect the difference from 50% to 80% in the primary endpoint, the accrual goal of this study was re-calculated to ensure 149 patients in the intervention arm, assuming 16 sites enrolling patients for this trial (8 to the non-intervention group (Arm A) and the other 8 to the intervention group (Arm B)). Patients from each site will be enrolled into one of the four strata depending on the patient's pregnancy status, sexual activity status, and/or her birth intention. Given some sites accrue much faster than the others, a NCORP accrual cap of 45 patients was implemented per Addendum 8.

As of January 4, 2021, 268 patients from 9 Arm A sites and 138 patients from 8 Arm B sites have had been enrolled to this trial. As this is a comparative study, the trial will continue accrual for both arms until Arm B meets its accrual goal of 149 patients which is projected to take another 5 months. Taking into account the site accrual up to January 4, 2021 and the accrual rate in the past three months (i.e., the last three months of 2020, with the top three accrual sites met the accrual cap of 45 patients and closed accrual to Arm A), the final accrual of this study, thus, is expected to be 425 patients (276 from Arm A and 149 from Arm

Rev. Add11

Rev. Add8
Rev. Add9

B). The mean cluster size is projected to be 25 patients assuming 17 enrolling sites in total (~30 patients per cluster for Arm A and ~18 patients per cluster for Arm B). As suggested by Table 1, this study is equipped with more power if the cluster size is larger than the average of 18-19 patients per cluster and/or if the number of clusters per arm is greater than the stated 8 sites per arm in the sample size calculations. The additional patients and sites in Arm A imply the power of this study will be a little larger than stated (i.e., 85% power) to detect a change from 50% to 80% on the primary endpoint with the projected final accrual of 425 patients.

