8.6 Analysis Plan

8.6.1 Plan for the primary objective
With a cluster randomized design, the generalized estimating equations (GEEs) method will be used to evaluate the intervention effect. The GEEs method can be used to construct an extension of standard logistic regression²⁷. For the primary endpoint, appropriate reproductive health management, a GEE model with an exchangeable correlation structure (i.e., assuming every patient within a cluster is equally correlated with every other patient from that cluster) and registering institution as the cluster variable will be fitted to compare the rates between the intervention group and the no intervention group by combining patients in all strata. The appropriate reproductive health management rate at each time point will be summarized, by arm, with frequency and percentage along with its 95% confidence interval. This rate in the non-intervention arm will indicate whether reproductive health needs are adequately addressed (Hypothesis 1, Section [1.4.1](#)). Whether the intervention can improve reproductive health care (Hypothesis 2, Section [1.4.2](#)) can be determined by comparing this rate between the non-intervention arm and the intervention arm.

The same method will be used to evaluate the intervention effect on contraception usage for Stratum 1 and Stratum 2, separately. Since it is expected that contraception usage will be influenced by the number

of children (0, 1-2, >2), type of treatment (chemo vs. RT vs. surgery vs. combination), and disease stage (nonmetastatic vs. metastatic) as well, these factors will be included in the model as covariates. The contraception usage rate at each time point will be reported with frequency and percentage along with its 95% confidence interval. Similar analysis method will be applied to the proportion of patients with pregnancy by the end of 2 years after baseline visit on the study. The analysis will be applied to patients by stratum for each of these secondary endpoints.

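### The Arm A to Arm B enrolment mix changed over calendar time, but the primary GEE in section 8.6.1 has no enrolment-time term, so part of any time trend enters the arm contrast.

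*Combined protocol and SAP*

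**What the plan says.** Section 8.3 reports the cumulative split at 4 January 2021: "66% (268/406) of the enrollment is from sites on the control arm and 34% from sites in the intervention group". It adds, in parentheses, "with recent accrual closer to 50% in each group, due to site accrual caps". Section 8.4 gives the mechanism. The cap is described as "a NCORP accrual cap of 45 patients was implemented per Addendum 8", and the rate for the last three months of 2020 is given for a period in which "the top three accrual sites met the accrual cap of 45 patients and closed accrual to Arm A". Accrual continues in both arms "until Arm B meets its accrual goal of 149 patients which is projected to take another 5 months". The projected final count is 425, with 276 in Arm A and 149 in Arm B.

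The entry rules also changed during accrual. Section 8.4 states "we lowered the age limit to 15 years in Addendum 9 (effective from February 6, 2019", and pediatric NCORPs could then join.

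The primary analysis in section 8.6.1 is a GEE with exchangeable correlation that pools all strata, with "registering institution as the cluster variable will be fitted to compare the rates between the intervention group and the no intervention group". It names no covariate for the primary endpoint. The contraception models carry number of children, treatment type and disease stage. No model has an enrolment-time term, and no sensitivity analysis by enrolment period is described.

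**The concern.** Randomization was by institution (sections 5.1 and 8.7), so it balanced sites and not the dates on which sites supplied patients. Once large Arm A sites closed, the share of new patients coming from Arm B rose. Date of enrolment is then associated with arm. Arm A is usual practice (section 5.2.1), and nothing in the design holds usual practice constant over the years of accrual.

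A time trend common to both arms would cancel if both arms had the same spread of enrolment dates. They do not, so part of the trend appears as an intervention effect. Rising standards of care would flatter Arm B, and falling standards would count against it. Clustering by institution deals with correlation within sites and does not remove a timing imbalance between arms. Adjustment for stratum or age would not remove a change in practice either.

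**Working it through.** **Inputs.** From section 8.3: 268 and 138 enrolled; 8 clusters per arm, mean size 15, CV 0.8, ICC 0.10, two-sided alpha 0.10, target 50% to 80%. From section 8.4: final 276 and 149, five months remaining. Assumed: the size of the drift, and the length of any 1:1 phase beyond the dated one.

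**The plan's own figures.**
- 268/406 = 66.0%, as stated. 268/138 = 1.94:1, and 276/149 = 1.85:1 at the projected end.
- Design effect = 1 + ((0.8² + 1) × 15 − 1) × 0.10 = 3.36.
- SE of the difference = √[(0.5×0.5 + 0.8×0.2) × 3.36/120] = 0.107, and 0.30/0.107 = 2.80.
- With a t critical value of 1.761 on 14 df, power is 0.842, against 0.85 stated.
- 120/(0.95 × 0.85) = 148.6, which gives the plan's 149 per arm.

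**Bias formula.** Bias = (late share in Arm B − late share in Arm A) × drift. Shares use enrolled counts. They hold for evaluable patients if ineligibility and attrition do not differ by arm and period.

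**Late phase on the plan's rates.** The projected remainder is 276 − 268 = 8 in Arm A and 149 − 138 = 11 in Arm B over five months, or 1.6 and 2.2 per month. I apply these rates to the last three months of 2020 as well, eight months in all:
- Arm A: 12.8/276 = 4.6%
- Arm B: 17.6/149 = 11.8%

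**Results.**

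| Late phase | Late share A | Late share B | Difference | Bias, 10-point drift | Bias, 15-point drift |
|---|---|---|---|---|---|
| Plan's rates from October 2020 | 4.6% | 11.8% | 7.2 | 0.7 | 1.1 |
| 50 per arm (assumed) | 18.1% | 33.6% | 15.4 | 1.5 | 2.3 |
| 100 per arm (assumed) | 36.2% | 67.1% | 30.9 | 3.1 | 4.6 |

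**Simulation check.** GEEs with an identity link and exchangeable correlation were fitted to 300 trials per scenario, with site sizes assumed and no intervention effect. The Monte Carlo SE of the mean estimate was about 0.55 points, so the SD of the arm effect is about 0.55 × √300 = 9.5 points.
- 50 late patients per arm, 10-point drift: mean estimate 1.7 points without a period term and 0.0 with it.
- Late shares of 27% and 50%, 20-point drift: 5.1 points without and 0.3 with.
- Plan's rates: the bias is too close to Monte Carlo error to be resolved, and the formula is the better guide.

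A separate simulation used calendar year as the term, again with assumed site sizes. It removed 0.3 to 3.2 points of shift, and the SD of the arm effect stayed at about 9 to 9.5 points.

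**Test size.** By normal approximation with SE 9.5, a nominal 10% test rejects in P(Z > 1.645 − b/9.5) + P(Z < −1.645 − b/9.5) of trials, where b is the bias in points:
- b = 1.1: 10.2%
- b = 2.3: 11.0%
- b = 4.6: 14.0%

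**The case against.** **The bias may be trivial.** The only dated window for the near-equal split is the last three months of 2020. On the plan's rates the bias is then about one point, roughly a tenth of a standard error. The post-cap rate is 1.6 + 2.2 = 3.8 patients per month, so 100 late patients in total would take about 26 months. This stands as a limit on size. Earlier monthly rates are not given, so a longer phase is neither shown nor excluded.

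**The age change does not explain it.** A reader might link the lower age limit of 6 February 2019 to the change in ratio. The documents do not support this: the rule applied to both arms from one date, and accrual by arm before and after it is not reported. A split at that date might miss the shift altogether.

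**The term may be in Addendum II.** Section 8.1 refers to a statistical analysis plan there, which is not available for this review. It is cited for endpoint details, whereas the model itself is in section 8.6.1. The absence is established for section 8.6.1 only.

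What remains is that the arm mix demonstrably changed over time and the stated model does not allow for it.

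**Conclusion.** The point holds as a minor weakness of the analysis. It rests on documented facts about the changing arm mix and on the model as written in section 8.6.1. Its size rests on an assumed drift: 0.7 to 1.1 points for a drift of 10 to 15 points on the plan's rates, and 1.5 to 4.6 points if 50 to 100 patients per arm were enrolled at 1:1. Against a 30-point target and an SE of about 9 to 10 points, the estimate is affected more than the test. The nominal 10% level is nearly unchanged except at the largest assumed phase.

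Two stronger readings are tempting and should not be drawn:
- **That early accrual ran at more than 2:1.** The documents give 1.94:1 overall. Taking out the eight-month late phase leaves (276 − 12.8)/(149 − 17.6) = 263.2/131.4 = 2.00:1, and a higher ratio needs a longer late phase that is not documented.
- **That any drift would be read in full as intervention effect.** Only the drift times the difference in late share carries over, which is about 7% of it on the plan's rates.

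**What to change.** In section 8.6.1, add calendar year of registration as a fixed categorical term in the primary GEE and in the contraception GEEs, and report the fit without it alongside. State in advance how sparse first or last years will be merged, without reference to outcomes. Because a logistic GEE with a covariate changes the meaning of the odds ratio slightly, compare the two fits on the risk-difference scale. Do not use 6 February 2019 as the only split. A table of registrations by year and arm would let readers judge the imbalance directly.

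Registration dates are already held, so no new data are needed. The cost is SAP wording and one parameter for each year after the first, estimated mostly within sites. In a simulation of 500 trials per scenario with a single period term, the SE of the arm effect rose by 2% or less. The term should be written in before the outcome data are compared by arm.
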